5.2.3.4. Missing or Partial Dates for Recurrent Wheeze Event Start/ Stop Dates

In case of missing or partial dates of Recurrent Wheeze Event, same rules as for LRTI Hospitalization will be applied.

5.2.4. Handling of Plasma / Blood / Serum Concentrations that are Below the Lower Limit of Quantification

Not Applicable.

6. Statistical Methods

6.1. General Principles

All data processing, summarization and analyses will be performed using Fortrea's SAS Environment / Version 9.4 (or later) of the SAS® statistical software package.

The default summary statistics for quantitative variables will be the number of observations (n), mean, standard deviation (SD), median, minimum (min) and maximum (max), for those participants with data.

For qualitative variables, the number (n) and percentage (%) of participants with non-missing data per category will be the default summary presentation, and where appropriate and present, the number of missing values as a "Missing" category. Number of participants in the analysis population will be used as denominator for percentages calculation, unless otherwise stated in TFLs mock shell(s).

All statistical comparisons will be made using two sided tests at the $\alpha=0.05$ significance level unless specifically otherwise stated. All null hypotheses will be of no treatment difference. All alternative hypotheses will be two-sided.

Specifications for table, figure and data listing formats can be found in the TFL shells specifications for this study. Please refer to "2. General Format Guidelines" section within TFL shells for more details on presentation of results.

All analyses in the SAP will be carried out for all countries combined and as subgroup analyses by country.

6.2. Participant Disposition and Data Sets Analyzed

Participant disposition will be summarized by treatment group and overall, where appropriate, for the All Screened Set. The following information will be reported:

- Number of participants for the following categories:
 - Screened
 - Screen Failure
 - Reason for Screen Failure (Eligibility Not Met; Withdrawal by Parent/LAR; Parent/LAR uncontactable between signing consent and proposed randomization; Other reason)

- Number and percentage of participants for the following categories:
 - Randomized
 - Treated
 - Not Treated
 - Completed the study
 - Ongoing in the study
 - Discontinued the Study
 - Reasons for study discontinuation (Adverse Event; Protocol Deviation; Withdrawal by Parent/Guardian; Lost to Follow-Up)

In addition, at the time of First Year Analysis and Second Year Analysis, number and percentages of participants who continued until 24 Months Follow-up phase will be provided.

Above table will also be produced

- by country
- in participants who received Beyfortus as a routine medication if there are at least 10 concerned participants (First Year Analysis only)
- in UK reconsented participants (Second Year Analysis only)
- in UK reconsented participants who received Beyfortus as a routine medication if there are at least 10 concerned participants (Second Year Analysis only).
- Number and percentage of participants included in, and excluded from, each study population together with the reasons for exclusion from the analysis set. This table will also be produced in UK reconsented participants (Second Year Analysis).
- Number and percentage of participants who failed screening prior to randomization, including detail for screen failure
- Number and percentage of participants at each country / site. This table will also be produced in UK reconsented participants (Second Year Analysis).
- Number and percentage of participants by stratification factor; Each stratification variable will be presented by the stratum collected in Interactive Response Technology (IRT) system. This table will also be produced in participants who received Beyortus as a routine medication if there are at least 10 concerned participants (First Year Analysis only), in UK reconsented participants (Second Year Analysis) and in UK reconsented participants who received Beyortus as a routine medication if there are at least 10 concerned participants (Second Year Analysis).

A participant will be regarded as having completed the study if the status recorded on the Subject Status Technical Form eCRF form is “Study Completed”. A participant will be considered as having discontinued the study if they have an eCRF status of study discontinuation. Otherwise, the participant will be considered as ongoing in the study. However, at the time of First Year Analysis:

- UK participants who declined reconsenting will be considered as having “Completed the Study”. Completion date will be the 12 Month Follow Up Call date.
- UK participants who completed 12 Month Follow Up Call but didn’t re consent yet will be considered as “Ongoing in the Study”
- UK participants who already re consented will be considered as “Ongoing in the Study”.

A listing of all participants with their treatment and study completion status, including the reasons for study discontinuation, will be presented for the All Randomized Set as well as:

- in participants who received Beyfortus as a routine medication (First Year Analysis only)
- in UK re consented participants (Second Year Analysis only)
- in UK re consented participants who received Beyfortus as a routine medication (Second Year Analysis only).

A listing of all screen failed participants with their details for screen failure will be presented for the All Screened Set. A separate listing of participants who failed at least one inclusion / exclusion criteria including a text description of the criterion failed will be presented for the All Screened Set.

A listing of all randomized participants with their randomization details, including immunization date and actual treatment received will be presented for the All Randomized Set as well as:

- in participants who received Beyfortus as a routine medication (First Year Analysis only)
- in UK re consented participants (Second Year Analysis only)
- in UK re consented participants who received Beyfortus as a routine medication (Second Year Analysis only).

A listing of all participants excluded from at least one analysis set will be presented for the All Randomized Set.

6.3. Protocol Deviations

All important protocol deviations will be summarized for the All Randomized Set by treatment group and overall as described below (those leading to exclusion from the PPAS are detailed in Section 4.3.1):

- The number of unique participants with at least one important protocol deviation as well as the number of participants in each important protocol deviation category,

protocol deviation subcategory and protocol deviation study specific category will be presented by default descriptive summary statistics for categorical variables.

The summary will be sorted using numerical counts by descending order of protocol deviation category, then descending order of protocol deviation subcategory, then descending order of protocol deviation study specific category in the total column. Where groups or terms tie these will be sorted alphabetically.

A listing of all participants with one or more important / non important protocol deviations will be presented for the All Randomized Set.

6.4. Demographic and Other Baseline Characteristics

6.4.1. Demographic Characteristics

Demographic characteristics will be summarized for the All Randomized Set by treatment group and overall as described below. All missing data will be presented as part of a missing category, if appropriate. Standard descriptive statistics will be presented for the continuous variables of:

- Age (months)
- Weight (kg) at baseline
- Gestational age at birth (weeks)

Total counts and percentages of participants will be presented for the categorical variables of:

- Neonates (Yes/ No) defined as age ≤ 28 days
- Age group (months) derived from date of birth:
 - ≤ 3.0
 - > 3.0 to ≤ 6.0
 - > 6.0
- Sex
 - Male
 - Female
- Weight (kg) at baseline
 - < 5 kg
 - ≥ 5 kg
- Gestational age at birth (weeks)
 - < 37 weeks
 - ≥ 37 weeks
- Country
 - France
 - Germany

- United Kingdom

Age is collected in eCRF provided by the IRT system in calendar days.

Age (months) will be calculated as (randomization date – date of birth+1)/30.4375.

Demographic characteristics will be listed for the All Randomized Set.

Demographic analyses and listing will also be performed:

- by country
- in participants who received Beyfortus as a routine medication (First Year Analysis only), if there are at least 10 concerned participants (table)/ one concerned participant (listing)
- in UK reconsented participants (Second Year Analysis only).
- in UK reconsented participants who received Beyfortus as a routine medication (Second Year Analysis only), if there are at least 10 concerned participants (table)/ one concerned participant (listing).

6.4.2. Medical History

Medical history is defined as any significant (ie, clinically relevant) condition that the participant may have had prior to enrollment in the study, including any chronic conditions diagnosed prior to entry in the study.

Medical history will be coded using the Medical Dictionary for Regulatory Activities (MedDRA) (version 25.0) and will be presented by System Organ Class (SOC) and Preferred Term (PT) and total.

Medical history records will be summarized for the All Randomized Set by treatment group and overall as follows:

- The number and percentage of participants with at least one medical history record will be presented.
- The number and percentage of participants with at least one medical history record within each primary SOC and PT will be presented. The summary will be sorted using the internationally agreed order for SOC and using descending order of overall numerical counts for PT. Where terms tie, these will be sorted alphabetically.

Medical history records will be listed by-participant and within-participant for the All Randomized Set.

Same analysis and listing will be provided:

- in participants who received Beyfortus as a routine medication (First Year Analysis only), if there are at least 10 concerned participants (table)/ one concerned participant (listing)

- in UK reconsented participants (Second Year Analysis).
- in UK reconsented participants who received Beyfortus as a routine medication (Second Year Analysis only), if there are at least 10 concerned participants (table)/ one concerned participant (listing).

6.4.3. Prior and Concomitant Medications

All medications will be coded using the WHO Drug Global Dictionary, Format B3 (Version March 2022), Anatomical Therapeutic Chemical (ATC) Classification codes.

Concomitant medications will be collected in the event of an AE. Reportable medications include medications that may affect the interpretation of safety data (eg, an antipyretic or analgesic that could have reduced the intensity or frequency of an AE).

All vaccines administered within 14 days before or after dosing/randomization should be reported as concomitant therapies. All medications administered within 14 days before or after admission of LRTI hospitalization will also be considered as reportable.

Reportable medications will be collected in the eCRF. Dosage, homeopathic medication, topical and inhaled steroids, as well as topical, ophthalmic, and ear treatments will not be recorded (except topical analgesics applied at the injection site of study intervention).

Prior medications and concomitant medications are defined as follows:

- Prior medications are those taken prior to screening with a stop date prior to the date / time of randomization (for no intervention group) / immunization (for nirsevimab group)
- Concomitant medications are those with a start date on or after the date / time of randomization (for no intervention group) / immunization (for nirsevimab group), or those with a start date before the date / time of randomization (for no intervention group) / immunization (for nirsevimab group) and either a stop date on or after the date / time of randomization (for no intervention group) / immunization (for nirsevimab group), or are ongoing at the end of the study

See Section 5.2.3 for imputation of missing or partial dates for medication.

Prior and concomitant medications will be summarized separately for the All Randomized Set by treatment group and overall as follows:

- The number and percentage of participants with at least one prior / concomitant medication will be presented
- The number and percentage of participants with at least one prior / concomitant medication within each Anatomical Group (ATC Level 1), Therapeutic Subgroup (ATC Level 2), Pharmacological or Therapeutic Subgroup (ATC4) and preferred term will be presented. The summary will be sorted using numerical counts by descending

order of Anatomical Group, then descending order of Therapeutic Subgroup, then descending order of preferred term in the total column. Where groups or terms tie these will be sorted alphabetically

In addition, the same type of tables (by ATC Level 1, ATC Level 2, ATC Level 4 and preferred term) will be provided for:

- All Concomitant Medications in participants who received Beyfortus as a routine medication if there are at least 10 concerned participants;
- All Vaccines given within 14 days before or after dosing/randomization;
- All Vaccines given within 14 days before or after dosing/randomization in participants who received Beyfortus as a routine medication if there are at least 10 concerned participants;
- Vaccines given within 14 days before or after dosing/randomization, restricted to the list in Appendix 2 (Section 8.2);
- Medications administered within 14 days before or after an LRTI hospital admission. The following medications will be considered for the analysis:
 - o medications with a start date within 14 days before or after an LRTI hospital admission,
 - o medications with a start date 14 days before an LRTI hospital admission but with a stop date within the 14 days before or after an LRTI hospital admissions
 - o medications with a start date 14 days before an LRTI hospital admission and still ongoing (no stop date)
- Medications administered within 14 days before or after an LRTI hospital admission in participants who received Beyfortus as a routine medication if there are at least 10 concerned participants;

Prior medications and concomitant medications will be listed separately for the All Randomized Set. In the listings, the relative start and stop day of prior / concomitant medication use will be calculated relative to the time of randomization (for no intervention group) / immunization (for nirsevimab group) and will be presented for those participants in All Randomized Set. If the concomitant medication is “Ongoing” at End of Study it will be indicated as such in the listing and the relative stop day will not be calculated. Only original dates will be presented in the listing even though the relative day may be based on an imputed date.

6.5. Measurements of Treatment Compliance

Not applicable in this study.

6.6. Efficacy

The main objective of the study is to assess the efficacy of nirsevimab in preventing RSV LRTI hospitalization through the RSV season compared to no intervention in all 3 countries combined. The primary and key secondary efficacy objectives will be assessed in the Primary Analysis by a hierarchical order. Only if the superiority for the primary endpoint is demonstrated, a superiority approach will be used to assess the efficacy of nirsevimab in preventing very severe RSV LRTI through the RSV season compared to no intervention in all 3 countries combined.

If the superiority for very severe RSV LRTI through the RSV season is demonstrated, a superiority approach will be used to assess the efficacy of nirsevimab in preventing RSV LRTI hospitalization through RSV season compared to no intervention in each country separately. For this, Bonferroni-Holm procedure will be used in the statistical analysis.

For other secondary objectives and exploratory objectives, no hypotheses will be tested and the analyses will be descriptive.

In case of missing or partial dates of LRTI hospitalizations or recurrent wheeze events, rules defined in section 5.2.3.3 and 5.2.3.4 will be applied.

In addition, following efficacy listings will be provided at the time of Primary Analysis and First Year Analysis:

- LRTI
- Very Severe LRTI
- LRTI Hospitalization

At the time of First Year Analysis only, below listings will also be produced:

- LRTI in participants who received Beyfortus as a routine medication
- Very Severe LRTI in participants who received Beyfortus as a routine medication

At the time of Second Year Analysis, following listing will also be provided:

- Recurrent Wheeze Events in the United Kingdom for Reconsented Participants

For all above listings, original dates will be presented even though the relative day and follow-up time (months) may be based on an imputed date.

6.6.1. Primary Efficacy Analysis

The primary efficacy variable is defined as the overall incidence of RSV LRTI hospitalization through the RSV season in healthy term and preterm infants in all 3 countries combined, measured by $1 - \text{incidence rate ratio}$.

The null hypothesis of $(1 - (CN / NN) / (CC / NC)) \times 100\% \leq 0\%$ will be tested against the alternative hypothesis of $(1 - (CN / NN) / (CC / NC)) \times 100\% > 0\%$ at the $\alpha=0.05$ significance level.

where:

- CN and CC are the numbers of RSV LRTI hospitalization through the RSV season in the nirsevimab and the no intervention groups, respectively.
- NN and NC are the total person-time contributed by participants randomized in the nirsevimab and the no intervention groups, respectively.

If a participant experiences multiple occurrences of the same primary endpoint, only the first episode will be considered.

The following rules will be applied in the calculation of the total person-time for the follow-up time:

- The start date for the follow-up will be the date of randomization for participants who are randomized to no intervention, the date of treatment dosing for participants who are randomized to nirsevimab and treated, and the date of randomization for participants who are randomized to nirsevimab but not treated.
- For the participants who have the primary endpoint at the cut-off date for the Primary Analysis, the end date for the efficacy follow-up will be the date of hospital admission if the cut-off date is before the end of RSV season; otherwise the participants will be censored at the end of RSV season.
- For the participants who do not have the primary endpoint at the cut-off date for the Primary Analysis (see section 6.7.8), the efficacy follow-up will be censored at the end date defined in the following:
 - for the participants who continue in the study and had contact for safety events, the end date for the efficacy follow-up will be the end of RSV season, the last available date with confirmation of no RSV LRTI hospitalization or the cut-off date whichever is earlier.
 - for the participants who discontinued from the study before the end of RSV season and had contact for safety events, see Table 2 in section 3.1.4.
 - for the participants who had no contact for safety events at all throughout the efficacy follow-up period, the end date for the efficacy follow-up will be date of randomization for participants who are randomized to no intervention, the date of treatment dosing for participants who are randomized to nirsevimab and treated, and the date of randomization for participants who are randomized to nirsevimab but not treated.

The total person-time for the follow-up time of each participant will be calculated as:

Person-months = (the end date - the start date + 1)/30.4375.

NN (days), the total person-time contributed by participants randomized in the nirsevimab, will be the sum of person-months for all the participants in the nirsevimab group. And NC (days), the total person-time contributed by participants randomized in the no intervention group, will be the sum of person-months for all the participants in the no intervention group.

The 2-sided 95% CI for the efficacy will be calculated by an exact method assuming a binomial distribution of the number of RSV LRTI hospitalizations in the nirsevimab group conditional on the total number in both groups (described by Breslow and Day⁷) accounting for the follow-up time post-dosing/randomization.

The superior efficacy of nirsevimab in preventing RSV LRTI hospitalization is concluded if the lower bound of 2-sided 95% CI of the efficacy is $> 0\%$. P-value will also be provided. The primary efficacy analysis of the primary endpoint will be performed with the All Randomized Set.

RSV season is the period of increased RSV infection. For the purpose of efficacy analyses, the start of the RSV season will be defined on a country-by-country basis and will be based on country-specific epidemiological surveillance and the cut-off date (28Feb2023, except for site parent contact and medical call center contact, for which the date of database lock for Primary Analysis will be used) will be used as end dates.

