9.1 Statistical Hypotheses

The primary and key secondary efficacy objectives will be assessed in the Primary Analysis (see Section 9.4 for details of the Primary Analysis) by a hierarchical order. Details on statistical methods are provided in Section 9.4.

For the primary objective, a superiority approach will be used to assess the efficacy of nirsevimab in preventing RSV LRTI hospitalization through the RSV season compared to no intervention in all 3 countries combined. Only if the superiority for the primary endpoint is demonstrated, a superiority approach will be used to assess the efficacy of nirsevimab in preventing very severe RSV LRTI through the RSV season compared to no intervention in all 3 countries combined, and no multiplicity adjustment is needed for this.

If the superiority for very severe RSV LRTI through the RSV season is demonstrated, a superiority approach will be used to assess the efficacy of nirsevimab in preventing RSV LRTI hospitalization through RSV season compared to no intervention in each country separately. For this, Bonferroni adjustment of 2-sided α (ie, 0.05/3) is used to correct multiple testing in 3 countries in the sample size calculation and Bonferroni-Holm procedure will be used in the statistical analysis. For other secondary objectives and observational objectives, no hypotheses will be tested and the analyses will be descriptive.

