6.6.4.2. RSV LRTI Hospitalization in Each Country

If the efficacy of nirsevimab in preventing very severe RSV LRTI compared to the no intervention is concluded, RSV LRTI hospitalization will be evaluated in each of the 3 countries. The same analysis as described above in Section 6.6.1 for the primary endpoint with Bonferroni-Holm procedure based on the adjusted p-values for the multiplicity adjustment will be used to calculate the efficacy on All Randomized Set in each country. The

superior efficacy of nirsevimab in preventing RSV LRTI hospitalization is concluded for the country if the adjusted p-value is < 0.05 . The p-values will be ordered from the smallest to the greatest for the 3 countries and give rank 1, to the smallest, and 3, to the greatest. Compare the first-ranked (smallest) p-value to the alpha level $0.05/(3+1 - \text{rank})$. If the p-value is smaller, reject the null hypothesis for this individual test and move to the p-value of the next rank. Otherwise, the hypothesis is not significant and stops the procedure. The testing stops with the first non-rejected null hypothesis. All subsequent hypotheses are non-significant. Only countries with adjusted p-values and the first country with non-significant adjusted p-value will be presented. Adjusted p-values will be computed using PROC MULTTEST in SAS.

At the time of First Year Analysis, the adjusted 2-sided 95% CI for the efficacy will also be calculated by an exact method assuming a binomial distribution of the number of RSV LRTI hospitalizations in the nirsevimab group conditional on the total number in both groups (described by Breslow and Day) accounting for the follow-up time post-dosing/randomization.

The algorithm for follow-up time is the same as that for follow-up time in Section 6.6.1.

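### SAP 6.6.1 states a directional hypothesis at alpha 0.05, against SAP 6.1, and the country claims in 6.6.4.2 rest on a p-value whose sidedness neither section gives

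*SAP*

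**What the plan says.** SAP 6.6.1 gives the hypotheses for the primary endpoint. Efficacy of 0% or less "will be tested against the alternative hypothesis of" efficacy above 0%, "at the $\alpha=0.05$ significance level". The same section then bases the conclusion on an interval: superior efficacy "is concluded if the lower bound of 2-sided 95% CI of the efficacy" is above 0%. It adds that a p-value will be reported, without defining it or giving its sidedness.

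SAP 6.1 sets the general rule: "All statistical comparisons will be made using two sided tests at the" 0.05 level, unless a section specifically says otherwise. It continues: "All alternative hypotheses will be two-sided".

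For the country endpoint, SAP 6.6.4.2 reuses the 6.6.1 analysis with a "Bonferroni-Holm procedure based on the adjusted p-values for the multiplicity adjustment". The "superior efficacy of nirsevimab in preventing RSV LRTI hospitalization is concluded for the country if the adjusted p-value is" below 0.05. Sidedness is not mentioned. The adjusted 2-sided CI appears in 6.6.4.2 only for the First Year Analysis. SAP 3.3.5 says that a Bonferroni-adjusted 2-sided CI will be shown, gives no timing, and leaves the superiority decision to Holm.

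The protocol differs. Section 9.4.3.2 applies Holm to adjusted CIs and concludes superiority when the lower bound exceeds 0%. On sizing, section 9.1 states that "Bonferroni adjustment of 2-sided α (ie, 0.05/3) is used to correct multiple testing in 3 countries", with Holm for the analysis.

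**The concern.** A null of 0% or less against an alternative above 0%, tested at 0.05, is in ordinary usage a one-sided test at 5%. For the primary and very severe endpoints the wording has no effect, because the 2-sided 95% CI decides both (SAP 6.6.1 and 6.6.4.1) and allows 2.5% in the favourable direction.

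The country endpoint lacks that protection. It is a confirmatory key secondary endpoint, and the SAP decides it on a p-value alone. The protocol's adjusted-CI rule would have fixed the sidedness. The SAP moved to p-values, and its section 7 does not list the change. A programmer feeding three country p-values to the Holm routine therefore has two statements to follow: 6.1, which gives a two-sided p, and the hypothesis in 6.6.1, which gives a one-sided p. The thresholds are the same either way, so the choice sets how much error is allowed in favour of nirsevimab, and it can change a country's result.

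**Working it through.** **Inputs.** Control incidence 1.1%, 60% efficacy, 9,620 participants and 74 events per country, 90% power, 2-sided alpha 1.66% (protocol 9.2, SAP 2.3). Allocation is 1:1, so 4,810 per arm. Very severe incidence 0.4% in controls (same sections). Holm thresholds 0.05/3, 0.05/2 and 0.05 (SAP 6.6.4.2).

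**1. Reproduce the planned size.** With p1 = 0.011, p2 = 0.0044 and mean 0.0077:

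- n per arm = [z(α/2)·√(2·0.0077·0.9923) + z(β)·√(0.011·0.989 + 0.0044·0.9956)]² / 0.0066²
- Two-sided 1.66%: (2.395·0.12362 + 1.282·0.12353)² / 0.0066² = 4,741 per arm, or 9,482 per country. The plan's 9,620 is 1.4% higher, and 4,810 per arm gives 90.5% power.
- Expected events: 4,810 × (0.011 + 0.0044) = 74.07.
- Freedman's formula: (1.4/0.6)² × (2.395 + 1.282)² = 73.6, so 74 events. Schoenfeld's formula gives 65; the plan names no method.
- One-sided 1.66%: 4,080 per arm (8,160 per country), Freedman 64 events.

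The plan's figures reproduce with a two-sided alpha and not with a one-sided one.

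**2. Allowed error under each reading.** With two-sided p-values, the Holm thresholds 0.0167, 0.025 and 0.05 allow 0.0083, 0.0125 and 0.025 in the favourable direction, so the family is held at 2.5%. With one-sided p-values the same thresholds allow 0.0167, 0.025 and 0.05, so the family is held at 5%. At the first step, for three independent null countries: 1 − (1 − 0.05/6)³ = 2.48% against 1 − (1 − 0.05/3)³ = 4.92%.

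**3. Exact cut-offs at 74 events.** With equal person-time, the nirsevimab count given the total is Binomial(74, 0.5) under the null. The largest count that rejects, with its actual error in the favourable direction:

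| Holm step (threshold) | Two-sided p | One-sided p |
|---|---|---|
| First (0.0167) | 26 (0.70%) | 27 (1.33%) |
| Second (0.025) | 26 (0.70%) | 28 (2.37%) |
| Last (0.05) | 28 (2.37%) | 29 (4.03%) |

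Example: 27 v 47 events gives one-sided p = 0.0133 and two-sided p = 0.0265. At the first and second steps the one-sided value passes and the two-sided value fails. At the last step both pass; there the split falls at 29 v 45, with one-sided p = 0.0403 and two-sided p = 2 × 0.0403 = 0.081.

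**4. Chance of any false country claim, simulated.** 400,000 runs; independent Poisson counts with 4,810 per arm per country and equal person-time; very severe cases a share 0.4/1.1 of hospitalizations; only claims in favour of nirsevimab counted. The right-hand columns require the primary and very severe tests to succeed first on their 2-sided 95% CIs.

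| True efficacy by country | Countries alone: two-sided | Countries alone: one-sided | After preceding tests: two-sided | After preceding tests: one-sided |
|---|---|---|---|---|
| 0, 0, 0 | 1.89% | 3.85% | 0.15% | 0.24% |
| 60%, 0, 0 | 1.91% | 3.87% | 1.00% | 1.87% |
| 60%, 60%, 0 | 1.85% | 3.91% | 1.73% | 3.59% |
| 80%, 80%, 0 | 2.00% | 4.06% | 1.99% | 4.04% |

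The preceding tests almost remove the risk when nothing works. They give little protection to one null country when the other two are effective, which is the case that Holm is there to control.

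**The case against.** The strongest reply is that the SAP never says one-sided. Every explicit statement of sidedness in the two documents is two-sided: the 6.1 default, the CI in 6.6.1, the CIs in SAP 3.3.5, and the sizing in protocol 9.2. In 6.6.1 the promise of a p-value comes straight after the CI rule, so the natural reading is the p-value that matches that interval. The exception allowed in 6.1 is attached to its sentence on tests and significance level; the sentence on alternatives carries no exception. This stands, and it rules out three stronger readings.

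- A reader might infer that the SAP sets a one-sided test and so doubles the false country claims. The documents do not support that. They contain a contradiction, and the doubling follows only if it is resolved in favour of the literal 6.6.1 hypothesis.
- A reader might infer that no country CI exists before the First Year Analysis. Section 6.6.4.2 defers only the adjusted CI; the 6.6.1 method that it reuses includes the unadjusted 2-sided 95% CI, and SAP 3.3.5 sets no date.
- A reader might take 3.9% v 1.9%, with all countries null, as the size. That ignores the required success on two earlier endpoints, after which the figures are 0.24% v 0.15%.

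The reply does not remove the defect. The country rule is a p-value rule, its p-value is not defined where it is used, and the section that it refers to states a directional hypothesis at 0.05.

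**Conclusion.** The point holds as an internal contradiction in a confirmatory decision rule, of low to moderate severity. The 6.6.1 hypothesis disagrees with SAP 6.1, with its own CI rule and with the protocol's 2-sided alpha. The primary and very severe conclusions are the same under either reading. For country claims, the literal 6.6.1 reading raises the allowed favourable-direction familywise error from 2.5% to 5%. In the simulation, after the preceding tests, this is about 3.6% v 1.7% with two countries at 60% efficacy and one null, and 0.24% v 0.15% with all three null. Even on that reading Holm keeps the family within 5% one-sided. Under the 6.1 default there is no inflation.

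The sizes rest on the planned numbers per country, equal person-time, independent countries, and a very severe share of 0.4/1.1. Actual event counts would move the exact cut-offs but not the factor of two in the nominal limits.

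**What to change.** - In SAP 6.6.1, state the test as two-sided at 0.05 (or one-sided at 0.025), and define the reported p-value as the two-sided exact conditional p that matches the 95% CI, that is, twice the smaller tail if the interval is equal-tailed.
- In SAP 6.6.4.2, state that this two-sided p enters Holm and that superiority also requires an estimate above 0%, so that the rule agrees with the protocol's adjusted-CI rule. List the move from adjusted CIs to adjusted p-values in section 7.
- The SAP is version 6.0 of 14 January 2025, and the Primary Analysis was due by 30 April 2023 and is described in section 7 as done. Confirm in writing that the country p-values used there, and in its rerun at the First Year Analysis, were two-sided. If they were not, recompute the Holm decisions with two-sided values.

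The cost is two sentences, one entry in section 7 and a check of the program. No new data are needed.
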